#### **8.3. Withdrawal of individual subjects**

Subjects can leave the study at any time for any reason if they wish to do so without any consequences. The investigator can decide to withdraw a subject from the study for urgent medical reasons.

#### **8.4. Replacement of individual subjects after withdrawal**

Patients will be asked to participate in this project when treated in this time period up to a maximum of 40 patients .

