#### *Patient population*

As many of our EC patients are older and have cardiopulmonary problems as a result of their age, co-morbidities or lifestyle habits, we would like to compare a cohort of patients treated for EC who did or did not undergo (chemo)radiotherapy.

A cohort of these patients is available, as neo-CRT has become standard treatment since 2012 after the publication of the so-called CROSS trial, demonstrating an important survival benefit in the group that received neo-CRT followed by surgery compared to patients treated with surgery alone. During this time period and the time period shortly before and after, patients were treated either with or without neo-CRT. In this time period we did not select patients on cardiopulmonary co-morbidities or age, so we expect comparable groups. Part of these patients were already retrospectively analyzed and compared on short term (within 90 days) morbidity and mortality after resection [23]. These data were published in 2013. We demonstrated an increased incidence of pneumonia and rhythm disorders in patients treated with neo-CRT, but no difference was noted in neither hospital and intensive care unit stay nor in mortality or overall morbidity between these two groups. As these patients were treated in the time period 2000-2012 and thus will have a 5-15 years follow up there is a sufficiently large patient cohort available to prospectively analyze clinical and subclinical cardiac changes and/or toxicities.

*Which tests would be interesting at longer follow up or study parameters*

As mentioned in the introduction, the main focus of this study is (subclinical) cardiopulmonary (dys)functioning. The most important late (subclinical) toxicities we expect to find at longer follow up are: diastolic dysfunction, coronary artery disease, cardiac wall motion disorders, heart failure, pulmonary hypertension, pericardial effusion and/or constriction, cardiac arrhythmia and valve disorders. A number of these endpoints will eventually result in heart failure.

- Anamnesis and physical examinations will be performed in these patients
- In case a pulmonologist or cardiologist has been consulted, additional information will be collected from hospital records of these specialists.
- Radiotherapy treatment parameters will be collected from our database in case the patient was treated with radiotherapy.
- 6 minute walking test
- Echocardiogram
- CT scan
- Cardiac MRI scan
- ECG

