## **6. STUDY POPULATION**

### **6.1. Population (base)**

Patients with EC treated with or without neo-CRT, alive without evidence of disease, treated between 2000 and 2012 at the University Medical Centre Groningen will be eligible. Twenty patients will be included in both treatment groups. Length of follow up after treatment does not seem to be an important confounding factor as surgery is not considered to be an important risk factor for late toxicity.

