## 7. SAMPLE SIZE CALCULATION

As this is a pilot study to determine (sub-clinical) cardiopulmonary toxicity, a total of 40 patients, 20 in each group, will be included in this study.

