## 8. METHODS

### 8.1. Randomisation, blinding and treatment allocation

Not applicable

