### 8.2. Study procedures

Candidates will be selected from the surgical and radiotherapy database. General practitioners will be checked for their survival status. An introduction letter, including patient information for this study, will be sent to the surviving patients to explain the study and ask them to consider participation in this research project. Patients are given the opportunity to call the researcher for further information and questions about the study. Patients can give their informed consent by sending the written informed consent. After receiving the informed consent, appointments will be made whenever possible on one day in consultation with the patient.

- Interview and physical examination 45 minutes
- 6 minute walking test plus explanation 30 minutes
- ECG 15 minutes
- Laboratory tests 5 minutes
- Echocardiogram 30 minutes
- Cardiac CT scan 10 minutes
- Cardiac MRI scan 40 minutes

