### **11.2. Recruitment and consent**

Candidates will be selected from the surgical and radiotherapy database. General practitioners will be checked for their survival and disease status. An introduction letter and patient information sheet explaining the purpose and procedure of this study will be sent to the patients. Patients are given the opportunity to call or email the researcher for further information and questions about the study. Patients can give their informed consent by sending the written informed consent. If a patient has not given an answer within two weeks after receiving the letter, we will send a second letter as a reminder. After we receive the consent the appointments will be made on whenever possible on one day in consultation with the patient.

Patients consent will be noted on an informed consent form compliant with the local and ethical regulations.

If during the study the patient for whatever reason no longer wishes to participate, he/she can withdraw his/her consent at any time.

Prior to the start of the study, the protocol has to be approved by the medical ethics review committee of the participating institution. Approval will be indicated in writing with reference to the final protocol number and date.

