### **11.4. Benefits and risks assessment, group relatedness**

The risk of participation in this study is very low. Patients have to visit the hospital once. The patient will have to stay in the hospital for approximately 6-8 hours. Within this time period anamnesis, questionnaires, physical examination and additional tests will be performed.

Blood withdrawal may result in local tenderness or hematoma, which are self-limiting.

Cardiac MRI scan requires IV contrast infusion with gadolinium, with the use of gadolinium there is a very low risk of anaphylactic reactions, nausea and headache, besides, the small bore used in MRI scanning may trigger claustrophobic feelings

Echo, ECG and the walking test do not cause any harm to the patients.

CT scan will give radiation exposure but as the total dose of this cardiac CT scan is relatively low total radiation dose of 0.6 mSv (less than a third of the annual background radiation dose), the risks will be minimal.

Patients participating will be evaluated for subclinical cardiopulmonary (dys)functioning. Patients will be referred to a cardiologist or pulmonologist for early intervention if considered necessary, this might improve quality of life or even life expectancy.

The results of this pilot study will form the basis for a subsequent prospective observational cohort study in which the most promising tests and clinical endpoints will be used to assess correlations with radiotherapy dose metrics with the ultimate aim to develop prediction models. These models can be used for model-based radiotherapy treatment plan optimization and to select patients for the best radiation technique, e.g. proton therapy.

Furthermore, the result of such a prospective cohort study might indicate the necessity of preventive measures for cardiopulmonary toxicity in the future.

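### The expectation of comparable groups covers only how treatment was chosen, yet Protocol section 10.1 compares 20 v 20 self-selected survivors with an unadjusted t-test

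*Protocol*

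**What the plan says.** The groups are not randomised; section 8.1 on allocation reads "Not applicable". Size is fixed in section 6.1 ("Twenty patients will be included in both treatment groups") and section 7 ("a total of 40 patients, 20 in each group, will be included in this study").

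Candidates come from the surgical and radiotherapy databases. Under section 8.2 a letter "will be sent to the surviving patients to explain the study and ask them to consider participation in this research project". Section 11.2 adds one reminder: "If a patient has not given an answer within two weeks after receiving the letter, we will send a second letter as a reminder". The cap is stated in section 8.4, under replacement: "Patients will be asked to participate in this project when treated in this time period up to a maximum of 40 patients". Section 11.4 describes what is asked of participants: "The patient will have to stay in the hospital for approximately 6-8 hours".

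The argument for comparability is in section 1, under Patient population: "In this time period we did not select patients on cardiopulmonary co-morbidities or age, so we expect comparable groups".

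Section 10.1 compares cardiopulmonary parameters between the groups by an independent t-test, with Bonferroni correction where it applies. Section 10.2 tabulates risk factors and tests them between groups, also by t-test. Section 4 lists age, sex and the main cardiac risk factors among the data collected.

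**The concern.** The comparability argument concerns treatment decisions taken between 2000 and 2012. Three later filters decide who is analysed, and each may be related to cardiopulmonary status, which is the outcome:

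- being alive and free of disease (section 6.1);
- having no pacemaker or other contraindication to MRI (section 6.3);
- agreeing to the test day (sections 8.2 and 11.4).

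Nothing in the argument says that these filters act alike in both groups. Even if they did, 20 per group is small enough for chance to leave the groups clearly different on age or another risk factor.

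The group difference is part of the primary objective in section 2. Section 1 itself gives age, co-morbidity and lifestyle as the reason why a comparison group is needed. If the groups differ on age, the t-test in section 10.1 attributes the age effect to neo-CRT or lets it mask an effect. Section 11.4 says that the results will guide the choice of tests and endpoints for the next cohort study, so a test could be kept or dropped because of who took part.

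**Working it through.** The Protocol gives no effect size, SD, power or response rate. There is no planned figure to reproduce beyond 40 = 2 x 20. Inputs not in the document are marked as assumed.

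**1. Chance imbalance in age, with identical source populations.**
The standard error of the difference in means is SD x sqrt(2/20) = 0.316 SD, and the 95% range is ±1.96 times that.

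| Age SD (assumed) | Standard error | 95% range of the difference |
|---|---|---|
| 6 years | 1.90 | ±3.7 years |
| 8 years | 2.53 | ±5.0 years |
| 10 years | 3.16 | ±6.2 years |

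A continuous factor differs by more than 0.5 SD with probability 2 x [1 − Φ(0.5/0.316)] = 0.11. With 5 to 9 independent factors, at least one does so with probability 1 − (1 − 0.114)^5 = 0.45 to 1 − (1 − 0.114)^9 = 0.66. For a binary factor with true prevalence of 20% to 50% (assumed), the groups differ by 20 points or more with probability 0.16 to 0.27 (exact binomial).

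**2. What the section 10.2 test can show.**
The two-sided 5% critical value on 38 degrees of freedom is 2.024. At SD 8, an observed age difference of up to 2.024 x 2.53 = 5.1 years is therefore non-significant. For a true imbalance of 0.5 SD (4 years at SD 8), the noncentrality is 0.5 x sqrt(20/2) = 1.58 and the power is 0.34. For a risk factor present in 50% v 30%, the power is about 0.25.

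**3. What an age imbalance does to the unadjusted comparison.**
If an endpoint has within-group correlation r with age, an age difference of k SD shifts the endpoint difference by r x k SD. At the edge of the chance range, k = 1.96 x 0.316 = 0.62.

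| r (assumed) | Shift in endpoint at k = 0.62 | Standard error after adjusting for age, sqrt(1 − r²) |
|---|---|---|
| 0.2 | 0.12 SD | 0.98 of unadjusted |
| 0.4 | 0.25 SD | 0.92 of unadjusted |
| 0.5 | 0.31 SD | 0.87 of unadjusted |

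Age and sex as covariates reduce the residual degrees of freedom from 38 to 36.

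**4. Self-selection (all response rates assumed).**
Let 40% of both groups truly have dysfunction. The prevalence among responders is 0.4a / (0.4a + 0.6h), where a and h are the response rates of affected and unaffected patients.

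- a = 40%, h = 60%: 0.16/0.52 = 31%. If this holds in one group only, the gap is −9 points. If it holds in both, the gap is zero.
- a = 30%, h = 60%, one group only: 0.12/0.48 = 25%, a gap of −15 points.
- a = 60%, h = 40%, one group only: 0.24/0.48 = 50%, a gap of +10 points.
- True prevalences of 20% and 40%, with a = 40% and h = 60% in both groups: 0.08/0.56 = 14% and 31%. A true gap of 20 points becomes 16.5.

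The result runs from no distortion to distortion in either direction, depending wholly on assumed rates.

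**The case against.** A reader might infer that recruitment builds in a spurious difference of some 9 points. The document does not support that. The burden of the visit and the prospect of referral are the same in both groups, no mechanism is stated by which response would differ, and the gap appears only when distorted response is assumed on one side.

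A reader might also infer that nothing is known about decliners, so that bias could never be examined. That goes too far as well. Candidates are drawn from existing databases, which identify those who decline. The Protocol is silent on comparing them with participants, but it does not rule this out. Only reasons for refusal would be lost if not noted at the time.

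Nor are the section 10.2 t-tests the only check. Section 4 records a broad set of risk factors, the frequency tables show imbalance whatever the p-value, and section 8.2 uses pre-treatment coronary calcium to estimate baseline risk. No passage says that a non-significant test will be taken as proof of comparability.

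Further, "up to 40" must be read with the quota of 20 per group: group sizes are fixed and only composition is open. This is an exploratory pilot, volunteer selection comes with any consent-based study, and an analysis plan that is not shown may add adjustment.

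All of this limits the point without removing it. The comparability inference still stops at treatment choice. Section 10.1 does not leave the method open: it states an unadjusted comparison for non-randomised groups. An adjusted analysis elsewhere would have to be reconciled with it.

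**Conclusion.** The point holds in limited form. Comparability at treatment choice does not carry over to the 20 v 20 analysed, and the unadjusted t-test relies on it doing so. The part that can be sized is chance imbalance: about ±5 years in mean age at an assumed SD of 8 (±3.7 to ±6.2 for SD 6 to 10), with 34% power in section 10.2 for a true imbalance of half an SD. An age imbalance at the edge of that range shifts an endpoint correlated 0.2 to 0.5 with age by 0.12 to 0.31 SD.

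Bias from response that differs by group is possible, but its size and direction cannot be computed, because the document gives no response rates, survivor numbers or prevalences. The figures for it show possibility, not likelihood. The change is worth making because it costs little.

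**What to change.** 1. **Section 10.1:** estimate each group difference, with confidence interval, from a linear model with group, age and sex. Both covariates are already collected. The cost is two degrees of freedom, and the standard error falls where age predicts the endpoint.
2. **Section 10.2:** judge balance by the size of the differences (standardised differences, or percentage points for binary factors), not by p-values.
3. **Sections 8.2 and 11.2:** tabulate responders against non-responders by group on age, sex, stage and treatment year from the existing databases, with the reason for refusal where one is given. This adds one table and a short log kept during mailing.
4. **Section 1, Patient population:** limit the comparability statement to treatment choice.

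Optionally, invite surgery-alone patients frequency-matched to the neo-CRT patients on age band and sex, where the pool of eligible survivors allows. Sparse bands may slow recruitment: the cohort is called sufficiently large overall, but not within bands. Neither matching nor adjustment for age and sex removes volunteering or refusal driven by symptoms; the responder table can only help to judge it.

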### **8.5. Follow-up of subjects withdrawn from treatment**

No further follow up is required.

## **9. SAFETY REPORTING**

### **9.1. Section 10 WMO event**

In accordance to section 10, subsection 1, of the WMO, the investigator will inform the subjects and the reviewing accredited METC if anything occurs, on the basis of which it appears that the disadvantages of participation may be significantly greater than was foreseen in the research proposal. The study will be suspended pending further review by the accredited METC, except insofar as suspension would jeopardise the subjects' health. The investigator will take care that all subjects are kept informed.

### **9.2. AEs, SAEs and SUSARs**

Adverse events, serious adverse events and suspected unexpected serious adverse reactions will not be assessed in this study as no clinical relevant adverse events, serious events and suspected unexpected serious adverse reactions are expected.

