## **12. DATA COLLECTION, DATA MANAGEMENT, MONITORING AND PUBLICATION**

### **12.1. Electronic case report forms**

Wherever possible, all data will be entered directly into the eCRF. Where needed, paper source documents can be used. An audit trail will maintain a record of initial entries and changes made; reasons for change; time and date of entry; and user name of person authorizing entry or change. For each subject enrolled, an eCRF must be completed and electronically signed by the principal investigator or authorized delegate from the study staff. If a subject withdraws from the study, the reason must be noted on the end of study form of the eCRF. The investigator should ensure the accuracy, completeness and timeliness of the data recorded in the eCRF and in all required reports.

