#### **12.8. Annual progress report**

The sponsor/investigator will submit a summary of the progress of the trial to the accredited METC once a year. Information will be provided on the date of inclusion of the first subject,

numbers of subjects included and numbers of subjects that have completed the trial, serious adverse events/ serious adverse reactions, other problems, and amendments.

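### Section 9.2 rules out assessing serious adverse events, section 12.8 promises the METC yearly information on them, and no systematic step collects that information

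*Protocol*

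**What the plan says.** Section 9.2 sets the rule: "Adverse events, serious adverse events and suspected unexpected serious adverse reactions will not be assessed in this study". It gives its reason in the same sentence: "as no clinical relevant adverse events, serious events and suspected unexpected serious adverse reactions are expected".

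Section 12.8 makes a commitment to the ethics committee: "The sponsor/investigator will submit a summary of the progress of the trial to the accredited METC once a year". The content of that summary includes "numbers of subjects included and numbers of subjects that have completed the trial, serious adverse events/ serious adverse reactions, other problems, and amendments".

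Section 11.4 describes the contrast agent used for the cardiac MRI: "with the use of gadolinium there is a very low risk of anaphylactic reactions, nausea and headache". The Summary likewise lists brief side effects and calls allergic reactions rare. The Cardiac MRI part of section 8.2 gives the dose, 0.2 mmol/kg gadoterate meglumine.

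Three other sections bear on whether an event would be recorded:
- Section 9.1 requires the investigator to inform the subjects and the METC of anything from which "it appears that the disadvantages of participation may be significantly greater than was foreseen in the research proposal".
- Section 8.3 lets the investigator withdraw a subject on pressing medical grounds, and section 12.1 adds: "If a subject withdraws from the study, the reason must be noted on the end of study form of the eCRF".
- Section 8.5 says of withdrawn subjects: "No further follow up is required".

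**The concern.** Section 9.2 removes the source of the data that section 12.8 undertakes to report. A site that follows 9.2 to the letter has no defined activity from which to fill in the serious-event line of the yearly summary.

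The stake is oversight of participants, not inference. The study gives a contrast agent for research purposes to survivors of oesophageal cancer. By the account in section 1, many of the centre's patients with this cancer are older and have cardiopulmonary problems. The protocol takes the contrast risk seriously enough to check eGFR before infusion (section 8.2, laboratory tests). The METC should be able to read a yearly statement about serious events as the result of someone having looked.

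**Working it through.** No formula applies. The protocol states no figure on this point, and the conflict depends on no rate, sample size or error level. The check is to set the sections side by side and ask, for each kind of event, which section would require a record.

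**Step 1: do the two statements conflict?** Section 9.2 says that serious adverse events are not assessed. Section 12.8 says that information on them is provided yearly. Neither carries a condition or refers to the other, and both are current text. They do not align.

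**Step 2: which events have a stated route?**

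| Event at the study visit | Section that applies | Record required? |
|---|---|---|
| Event after which the subject withdraws or is withdrawn | 8.3 with 12.1 | Yes, as the reason on the end of study form |
| Event showing harm significantly beyond what was foreseen | 9.1 | Yes, subjects and METC are informed |
| Serious event of a kind already foreseen, no withdrawal | None found | No |
| No event | None found | No, so no entry shows that anyone checked |

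**Step 3: is the third row a real possibility?** Section 11.4 names anaphylactic reactions as a known, very low risk of gadolinium. Because that risk is foreseen, a single case need not meet the threshold in 9.1. A patient who is treated, recovers and stays in the study triggers nothing in 12.1. So this event can occur without any section requiring a record of it.

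**Step 4: do other parts of the protocol cover it?**
- The passage at the end of section 8.2 on contacting the patient and general practitioner concerns abnormalities that the tests reveal, not reactions to the tests.
- The interview in section 8.2 covers medical history and existing complaints.
- Section 8.5 waives follow-up after withdrawal. It does not cancel the recording of the reason, and it adds no route.
- No section defines a serious adverse event for this study, sets a collection window or names a reporting form.

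**Step 5: does the stated reason resolve the conflict?** Section 9.2 relies on no clinically relevant events being expected. That can stand beside a very low risk in 11.4, so the two are not strict opposites. A low expectation supports light recording. It does not supply the information that 12.8 promises.

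**The case against.** The strongest case is that this is a mismatch of wording with little practical weight. The study is a single-visit, cross-sectional pilot with no study treatment, and section 9.1 is the immediate channel to the METC. Under section 11.2 the protocol needs ethics approval before the start, so the committee will have 9.2 before it and can read a yearly 'none' in that light. The summary under 12.8 also has room for other problems. Section 9.2 does not forbid staff from reporting an event that they see, and a severe contrast reaction may well end in withdrawal, which puts the reason on the eCRF. Finally, the conflict could be removed from the other side, by changing 12.8.

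Much of this stands, and it limits the point. A reader might infer that nothing at all in the protocol feeds the serious-event item, or that none of the 40 visits can leave an event record without withdrawal. The documents do not support either reading. Sections 8.3 and 12.1 together record an event that leads to withdrawal, and 9.1 can carry an exceptional event to the METC. The eCRF forms and the data management plan are not shown, so the absence of an event form cannot be stated as fact, though 9.2 makes one unlikely.

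What does not stand is that these routes settle the matter. Withdrawal on medical grounds is discretionary, 9.1 has a high threshold, and neither is a systematic collection step. Knowing about 9.2 would let the METC discount the yearly item but would not give it content. Nor is this a matter for a statistical analysis plan: such a plan cannot supply data that the protocol says are not assessed.

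**Conclusion.** The point holds as a conflict between two current sections. Section 9.2 as written leaves the serious-event item of section 12.8 without systematic data, and a foreseen serious reaction without withdrawal has no required record. The gap applies at all 40 planned visits.

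It would go too far to read this as evidence that a serious reaction is likely. The protocol gives no rate, only qualitative terms (very low, rare), and the conflict is the same whether or not a reaction occurs. No rate calculation is needed. No group comparison and no sample size is affected.

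The conclusion rests on the protocol text alone. It assumes that no document outside it, such as the eCRF specification, already provides an event record. If one does, 9.2 contradicts that document too and still needs the edit. The change should be made because it concerns oversight of participants and costs almost nothing, but it does not threaten the scientific results.

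**What to change.** In section 9.2, replace the statement that events are not assessed with wording such as: *Serious adverse events and contrast reactions during the study visit are recorded in the eCRF, with 'none' entered if there were none. Serious adverse events are reported to the METC as stated in section 12.8.*

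The cost is a small edit to 9.2 and one short eCRF entry per visit, 40 in all, nearly all of which should read 'none'. Minor effects, such as a bruise after blood sampling, need no entry.

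The alternative is to strike the serious-event item from 12.8, if the METC accepts an exemption. That removes the contradiction without a new form, but it leaves a foreseen contrast reaction without withdrawal unrecorded, so it is the weaker choice.
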